| Statistical analysis | 
All study variables will be presented by dose cohort and overall, using the appropriate descriptive statistics according to the variable nature, unless otherwise specified:
 
▪ continuous variables: number of non-missing observations, arithmetic mean, standard deviation (StDev), standard error (for PK variables), minimum, median, maximum (and geometric mean and its 90% confidence interval (CI) for PK variables).▪ categorical variables: number of non-missing observations and column percentages (N, %).▪ time to event variables: number of non-missing observations, number and percentage of censored observations, 1st quartile, median (and its 95% CI), 3rd quartile, Kaplan-Meier survival curves and event rate every two cycles, and at the End of Study Visit and at the End of Study, as appropriate. 
The behaviour over time of study variables will be summarized by treatment cohort and overall as follows:
 
▪ continuous variables: descriptive statistics for each time point and for the absolute/percentage differences to baseline. For PK variables, only descriptive statistics for each time point will be used.▪ discrete variables: descriptive statistics for each time point and shift tables to baseline. 
Pharmacokinetic Analysis
 
The PK analysis will be conducted on the PK population. All PK variables (i.e., serum concentrations and parameters) will be summarized by cohort using the following descriptive statistics
 |

[figure not shown]
when appropriate:

- number of non-missing observations (N),
- arithmetic mean and its 95% CI, StDev, coefficient of variation (CV%), and standard error (SE),
- geometric mean (GM) and its 90% CI and GM CV%,
- minimum, median, maximum.

The concentration of MEN1309 will be summarized for each scheduled sampling time point using descriptive statistics. Individual serum concentration data versus time will be presented in a data listing and visualized as individual concentration-time plots.

2.1 SCHEMATIC DESIGN : Dose Escalation and Cohort Expansion study design (AS EXAMPLE ONLY):

- **Step 1: Solid Tumors**, from 0.05 mg/kg up to MTD
- **Step 2: NHL**, from 0.80 mg/kg (or at lower level) up to MTD

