| | 
It is defined as the number of days between the first study drug administration and death from any cause. Patients without the event are censored to the last date of follow-up.
 
Progression free survival (PFS)
 
It is defined as the number of days between the first study administration to the date of first documented disease progression, relapse or death from any cause. Responding patients and patients who are lost to follow-up are censored at their last tumor assessment date.
 
Exploratory endpoints
 
▪ To determine the correlation between free CD205 at baseline with clinical activity of MEN1309.▪ To determine the correlation between CD205 expression and clinical activity of MEN1309. Protein expression will be assessed through IHC centrally evaluated on archived and, when available, new bioptic tissue samples.▪ To determine the Deoxyribonucleic Acid (DNA) sequence of CD205 at baseline.▪ To determine CD205 expression by flow cytometry on peripheral blood cells at baseline. |
| Immunogenicity Endpoints | 
▪ Incidence of anti-MEN1309 auto-antibodies. |
| Pharmacokinetic Endpoints | 
The following pharmacokinetic parameters will be assessed for MEN1309 and for total antibody (tAb), DM4 and its metabolite S-methyl-DM4, when applicable:
 
Maximum observed serum concentration (C_{max}), time to C_{max} (t_{max}), last quantifiable serum concentration value (C_{last}), time to C_{last} (t_{last}), pre-dose serum concentration (C_{trough}), apparent terminal elimination rate constant (k_e), terminal serum half-life ($t_{1/2}$), area under the serum concentration-time curves from time zero (pre-dose) to the time of the last quantifiable concentration ($AUC_{(0-t)}$), area under the serum concentration-time curve from time zero to infinity ($AUC_{(0-\infty)}$), percentage of $AUC_{(0-\infty)}$ obtained by extrapolation (%AUC_{ex}), systemic clearance (CL), volume
 |

| | |
|-----------------------------|--|
| | 
of distribution at steady state (V_{ss}), volume of distribution based on the terminal phase (V_d), area under the first moment curve from zero to infinity ($AUMC_{(0 \infty)}$), mean residence time (MRT), accumulation ratio (Ro) following repeated infusions.
 
PK parameters will be calculated after the first and second infusion of each dose cohort. C_{max} and C_{trough} will also be obtained after each administration of MEN1309.
 |

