6.2.2.3 Toxokinetics (TK)

6.2.2.3.1 *Exploratory single dose intravenous toxicity study of MEN1309 in cynomolgus monkeys was performed*

The TK of the ADC MEN1309 following a single dose intravenous infusion was investigated in 2 cynomolgus monkeys (1 male and 1 female) at 3 different escalating doses (1, 3, and 5 mg/kg). An observation period of 3 weeks was considered between the different administrations. No relevant gender-related differences were observed, and no relevant differences were observed between the concentrations of MEN1309 and those of the Total Antibody.

Finally, a 3-week interval between doses was sufficient to allow a complete clearance of the drug.

6.2.2.3.2 *Toxicokinetics of MEN 1309 following single and repeated administrations in cynomolgus monkeys*

Forty cynomolgus monkeys were randomly sorted in 4 treatment groups; each group, comprising 5 males and 5 females, was intravenously treated by 1 hour infusion for 3 times every 3 weeks with placebo, 0.1, 0.3, and 1 mg/kg of MEN1309, respectively.

The pharmacokinetics were non-linear, as a consequence dose-dependent terminal half-life and clearance were observed. Furthermore, with respect to conventional IgG, shorter terminal half-life and more extensive clearance were found. This evidence is in keeping with a possible TMDD to be mainly ascribed to the expression of the target antigen CD205 on some leukocyte populations. A reduced receptor-mediated ADC uptake in leukocytes could also be responsible for the long-lasting pharmacokinetic profiles observed in some animals.

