8.5.3 Pharmacokinetics Procedure and Assessment

Blood samples for MEN1309, tAb, DM4 and its metabolite S-methyl-DM4 serum concentration measurements will be taken before (pre-dose) and immediately after the end of each IV infusion during all cycles for each cohort. If any interruption occurs during MEN1309 infusion at any cycle, an additional blood sampling for PK will be taken at the time of each infusion interruption and just before each infusion resumption.

Furthermore, blood sampling for PK are obtained at 1, 2, 4, 6, 8, 10, 12, 16, 24, 36, 48, and 72 hours after the end of the infusion of Cycle 1 and Cycle 2 (see §2.4). For Cycle 2, PK blood sampling at 10, 12 and 16 hours after the end of infusion is informative but not mandatory.

For Cycles 3+, PK blood samples will be taken only before the start of infusion and immediately after the end of infusion, as well as in conjunction with any safety blood samples taken up to 72 hours after the end of infusion.

For dose levels higher or equal to 0.8 mg/kg, in case additional sampling for safety testing is required (e.g., between study visits), an additional blood sample for PK will also be taken at the same time. Moreover, only for dose levels higher or equal to 0.8 mg/kg, PK blood samples will be taken at Visits 2 and 3 of each cycle in conjunction with safety blood samples (see § 2.4).

The following pharmacokinetic parameters will be determined from the individual serum concentration-time curve for MEN1309, tAb, DM4 and its metabolite S-methyl-DM4, when applicable, using non-compartmental methods with Phoenix™ WinNonlin® software, version 6.4 or higher (Pharsight Corp., Mountain View, California).

| | |
|---------------------|--|
| C_{\max} | Maximum observed serum concentration. |
| t_{\max} | Time to C_{\max} . |
| C_{last} | Last quantifiable serum concentration value. |
| t_{last} | Time to C_{last} . |
| C_{trough} | Pre-dose serum concentration. |
| k_e | Apparent terminal elimination rate constant, estimated by log-linear regression analysis on serum concentrations visually assessed to be on the terminal log-linear phase. |
| $t_{1/2}$ | The terminal serum half-life, calculated according to the following equation: |
| | $t_{1/2} = \frac{0.693}{k_e}$ |
| $AUC_{(0-t)}$ | Area under the serum concentration-time curves from time zero (pre-dose) to the time of the last quantifiable concentration, calculated by means of the linear-log trapezoidal method. |

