| $AUC_{(0-\infty)}$ | Area under the serum concentration-time curve from time zero to infinity, calculated according to the following equation: |
| | $AUC_{(0-\infty)} = AUC_{(0-t)} + \frac{C_{\text{last}}}{k_e}$ |
| $\%AUC_{\text{ex}}$ | The percentage of $AUC_{(0-\infty)}$ obtained by extrapolation calculated as follows: |

$$AUC_{\text{ex}}(\%) = \frac{AUC_{(0-\infty)} - AUC_{(0-t)}}{AUC_{(0-\infty)}} * 100$$

| | |
|---------------------|--|
| CL | Systemic clearance, calculated according to the following equation: |
| | $CL = \frac{Dose}{AUC_{(0-\infty)}}$ |
| V_{ss} | Volume of distribution at steady state, calculated according to the following equation: |
| | $V_{ss} = CL * MRT$ |
| V_d | Volume of distribution based on the terminal phase, calculated according to the following equation: |
| | $V_d = \frac{Dose}{k_e * AUC_{(0-\infty)}}$ |
| $AUMC_{(0-\infty)}$ | The area under the first moment curve from zero to infinity calculated using the equation: |
| | $AUMC_{(0-\infty)} = \sum_{i=0}^{n-1} \frac{t_{i+1} - t_i}{2} (C_i t_i + C_{i+1} t_{i+1}) + \frac{t * Ct}{k_e} + \frac{Ct}{k_e^2} + \frac{t \cdot C_t}{\tau} + \frac{C_t}{\tau^2}$ |
| MRT | Mean residence time was calculated as: |
| | $MRT = AUMC_{(0-\infty)} / AUC_{(0-\infty)}$ |
| Ro | Accumulation ratio following 2 consecutive infusions calculated as: |
| | $Ro = AUC_{(0-t)}^{2nd} / AUC_{(0-t)}^{1st}$ |

PK parameters will be calculated after the first and second infusion of each dose cohort. C_{max} and C_{trough} will also be obtained after each administration of MEN1309. Actual PK sampling times will be used in the derivation of PK parameters. Alternatively, it is also acceptable to consider the planned sampling times if they do not deviate by more than 5% from the actual. Planned sampling times may be used as a replacement for unknown or missing actual times.

The calculation of the parameters listed above and others will depend upon the results of the drug concentration assay and the duration of drug infusions.

For the calculation of individual PK parameters, values Below the Lower Limit Of Quantification (BLOQ) will be handled as follows:

1. BLOQ values located before the t_{max} of their affiliating curve will be transformed to zero.
2. If a BLOQ value located after the t_{max} falls between 2 quantifiable concentrations, it will be omitted from the PK analysis.

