3. If, within a dosing interval, 2 or more BLOQ values occur in succession after quantifiable concentrations, the profile will be deemed to have terminated at the first BLOQ value and

94 of 126

any subsequent concentrations in that dosing interval will be omitted from the non-compartmental analysis.

4. In some circumstances, when a PK rationale exists, BLOQ values may be set to some other values, e.g., half of the Lower Limit of Quantification (LLOQ).

Concentrations reported as >LLOQ at time zero, when the patient has not previously been dosed, will be set to zero.

Exploratory PK/PD analyses may be carried out in order to investigate the relationship between drug exposure and clinical activity of the aforementioned analytes. Methods for these analyses will be described in the Data Analysis Plan included in the Statistical Analysis Plan (SAP).

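### Second-infusion CL, Vd and Vss use single-dose equations with no rule for residual first-infusion drug, so they would be understated if the Cycle 2 pre-dose sample is quantifiable

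*Protocol*

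**What the plan says.** The Protocol synopsis (Pharmacokinetic Endpoints), Protocol sections 8.5.3 and 8.5.5.5, and SAP section 5.1.1.5 all carry the same instruction: "PK parameters will be calculated after the first and second infusion of each dose cohort".

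Section 8.5.3 supplies one set of equations for both occasions:
- AUC(0-t) is the "Area under the serum concentration-time curves from time zero (pre-dose) to the time of the last quantifiable concentration", so it begins at the pre-dose sample.
- AUC(0-∞) adds Clast/ke to AUC(0-t).
- CL = Dose/AUC(0-∞), Vd = Dose/(ke × AUC(0-∞)) and Vss = CL × MRT.
- The accumulation ratio Ro is the second-infusion AUC(0-t) divided by the first.

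The only rule for a quantifiable value at time zero is: "Concentrations reported as >LLOQ at time zero, when the patient has not previously been dosed, will be set to zero". A quantifiable Cycle 2 pre-dose value is therefore kept. Neither document gives an AUC over the dosing interval, a subtraction of residual drug, a steady-state condition, or a different meaning of Dose for the second infusion. The PK part of SAP section 6.1.1.2 adds only summary statistics.

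**The concern.** The CL equation is exact when the dose in the numerator produced all of the area in the denominator. That is so after the first infusion. After the second, any first-infusion drug still present adds to the area but not to the dose, so CL comes out too low even if true clearance has not changed. Vd and Vss inherit the error.

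PK after single and repeated doses is a secondary objective (Protocol section 7.2), and the protocol gives reasons to look for a change between infusions. Section 6.2.2.3.2 describes non-linear kinetics with half-life and clearance depending on dose, and refers to "long-lasting pharmacokinetic profiles observed in some animals". A lower second-infusion CL in the tables could be read as a change in disposition when some or all of it was carry-over.

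**Working it through.** **No stated figure to reproduce.** The documents give no value for carry-over, second-infusion CL or Ro. As a check on the PK figures they do give, the exposure ratios in Protocol Table 1 reproduce: 23.61/0.671 = 35.2, 438.5/2.9 = 151.2, 6.45/0.671 = 9.6 and 44.2/2.9 = 15.2.

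**Inputs**
- Dosing interval: at least 21 days = 504 h (Protocol section 8.5.1).
- Infusion length: 3 h.
- Monkey half-life: 15 to 31 h at 3 and 5 mg/kg (section 6.2.2.2).
- Human half-life: not given. Every value above 31 h below is an assumption.
- PK sampling: to 72 h, plus Days 8 and 15 only at 0.80 mg/kg or more (sections 2.4 and 8.5.3).

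**Step 1: one-compartment linear model, true CL constant.** The share of a dose's exposure still to come after 504 h is r = 2^(−504/t½). By superposition, the second-infusion AUC(0-∞) is (Dose/CL) × (1 + r), so apparent CL2/CL1 = 1/(1 + r).

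| t½ | r | CL2/CL1 | Fall in CL |
|---|---|---|---|
| 31 h (monkey maximum) | 0.000013 | 1.000 | 0.001% |
| 3 days | 0.0078 | 0.992 | 0.8% |
| 5 days | 0.0544 | 0.948 | 5.2% |
| 7 days | 0.125 | 0.889 | 11.1% |
| 10 days | 0.233 | 0.811 | 18.9% |
| 14 days | 0.354 | 0.739 | 26.1% |

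A 5% fall thus needs a half-life of about 5 days, roughly four times the longest monkey value.

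**Step 2: the protocol's equations on its own sampling times** (3 h infusion, samples to Day 15). One compartment, t½ 7 days: CL, Vd and Vss ratios all 0.888 and Ro 1.126, in line with Step 1.

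**Step 3: two compartments (assumed parameters, samples to Day 15).** Ratios of second to first infusion; the last column subtracts Cpre/ke from the second-infusion AUC(0-∞), with Cpre the Cycle 2 pre-dose value.

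| t½ | CL | Vd | Vss | CL after subtraction |
|---|---|---|---|---|
| 6.0 days | 0.938 | 0.950 | 0.961 | 0.990 |
| 9.4 days | 0.850 | 0.889 | 0.903 | 0.961 |
| 13.6 days | 0.793 | 0.886 | 0.904 | 0.910 |

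Vd and Vss fall by less than CL. With samples to 72 h only, subtraction brings CL to 0.970, 0.925 and 0.904. With one compartment it restores CL2/CL1 to 1.000 at every half-life tried. The remaining gap arises because ke is estimated before the true terminal phase.

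**Step 4: what Table 1 implies.** With one compartment and infusion length T, Cmax ÷ (AUC/T) = 1 − exp(−kT).
- Human prediction, 0.05 mg/kg: 0.671/(2.9/3) = 0.694, k = 0.395 per h, t½ ≈ 1.8 h.
- Monkey, 1 mg/kg: 23.61/438.5 = 0.0538, k = 0.0553 per h, t½ ≈ 12.5 h.

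Monkey AUC rises 438.5/44.2 = 9.9-fold for a 3.3-fold dose increase, so Dose/AUC falls from 6.8 to 2.3 mL/h/kg. The documented half-lives are short, but they come from animals or a very low human dose in a system where clearance falls with dose.

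**The case against.** The strongest reply is that the documents point to little or no carry-over. Section 6.2.2.3.1 reports that three weeks, the trial's own interval, was enough for complete clearance; quoted monkey half-lives are 15 to 31 h; and Table 1 implies hours. Saturable clearance also speeds up as concentrations fall, so a linear model may overstate what remains at Day 21, and 21 days is only a minimum interval. This stands as to size: a reader might infer that second-infusion AUC does contain first-infusion drug, and the documents do not show that. It does not exclude carry-over. The complete-clearance statement comes from two monkeys, while the 40-animal study described next reports dose-dependent half-life and long-lasting profiles in some animals.

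A second reply is that carry-over would be visible. A reader might infer that it cannot be told apart from a true clearance change, but the documents do not support that. Ctrough is obtained at every administration and individual concentrations are listed and plotted (section 9.3.2). The Cycle 2 pre-dose value reflects the first infusion alone, so it shows directly whether drug remains. Ro is less useful, since it rises with carry-over and with a true fall in CL. What survives is that no stated step carries the trough into CL, Vd or Vss. The wording that parameter calculation depends on assay results gives no rule for this case either.

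Third, nothing turns on these values: they are descriptive summaries with no test or decision rule attached. That stands and limits the severity.

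**Conclusion.** The gap is real but minor. As written, a quantifiable Cycle 2 pre-dose value lowers second-infusion CL, Vd and Vss with nothing in either document to correct it. Whether that happens, and by how much, rests on a human half-life the documents do not give: about 0% at 31 h, 0.8% at 3 days, 5% at 5 days, 11% at 7 days and 19% at 10 days. These figures assume linear one-compartment kinetics and a 504 h interval, and saturable clearance could make them smaller. An equal fall in all three parameters is a one-compartment result; in the two-compartment examples Vd and Vss fell by less than CL. DLT and MTD are unaffected.

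**What to change.** In Protocol section 8.5.3 and the SAP PK section:
- Take CL, Vd, Vss, AUMC and MRT from the first infusion as the primary estimates.
- Report second-infusion values based on AUC(0-∞) uncorrected only when the Cycle 2 pre-dose value is BLOQ.
- When it is quantifiable, subtract Cpre/ke from AUC(0-∞) before computing CL and flag the result as approximate; otherwise report it as not calculated. Vd can use the corrected area. AUMC, MRT and Vss would also need the residual first moment removed (Cpre/ke² for one compartment); if that is not done, leave them uncalculated.
- As a supplement only, Dose/AUC over the actual second dosing interval may be added for patients at 0.80 mg/kg or more who have a Cycle 3 pre-infusion sample.

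The interval-based value should not replace the others. Patients who stop after Cycle 2 lack the closing sample, and lower doses have no planned samples between 72 h and the next pre-dose. In the linear model, second-interval AUC is (Dose/CL) × (1 − r²), so this CL is overstated by 1/(1 − r²) − 1: 1.6% at 7 days, 5.8% at 10 days and 14% at 14 days.

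The cost is a few sentences and no new samples. The downside is fewer, or only approximate, second-infusion CL, Vd, Vss and MRT values. First-infusion estimates are free of carry-over but still depend on the extrapolation with ke, so they should be read with %AUCex.

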2.2 STUDY FLOW-CHART

| PROCEDURE | Pre-screening Period Day -112 to Day -28 | Screening Visit Day -27 to Day -1 | STUDY VISITS | | | | | | | | Cycle 3+ Same study procedures as per Cycle 2 | End of Study Visit ¹ | Follow-up | | | | |
|--|---|--------------------------------------|----------------------|---------|-------------|----------------|---------|----------------|---|---------|--|---------------------------------|-----------|------------|---|---|--|
| | | | Cycle 1 | | | Cycle 2 | | | Day 1 | Day 2-4 | Day 8 & 15 | Day 1 | Day 2-4 | Day 8 & 15 | | | |
| | | | Visit 1 ^k | | Visit 2 & 3 | Visit 1 | | Visit 2 & 3 | | | | | | | | | |
| | | | Day 1 | Day 2-4 | Day 8 & 15 | Day 1 | Day 2-4 | Day 8 & 15 | | | | | | | | | |
| Informed consent and CD205 IHC analysis | X | | | | | | | | | | | | | | | | |
| Informed consent ^a | | X | | | | | | | | | | | | | | | |
| New Biopsy (optional) and CD205 IHC analysis | | X | | | | | | | | | | | | | | | |
| Inclusion/Exclusion criteria | | X | X | | | | | | | | | | | | | | |
| Demographics | | X | | | | | | | | | | | | | | | |
| Medical, surgical and medication general history | | X | | | | | | | | | | | | | | | |
| Tumor/NHL assessment ^b | | X | X | | | | | | | | | | | | X | | |
| Ophthalmic visit ^c | | X | | | | | | | | | | | | | | | |
| Dermatologic visit ^c | | X | | | | | | | | | | | | | | | |
| Physical examination | | X | X | X | X | X | X | X | | | | | | | X | | |
| Vital signs ^d | | X | X ^d | X | X | X ^d | X | X | | | | | | | X | | |
| ECOG PS | | X | X | | | X | X | | | | | | | | X | | |
| Weight measurement | | X | X | | | | | X | | | | | | | | | |
| ECG ^e | | X | X ^e | | | | | X ^e | | | | | | | | X | |
| Urinalysis | | X | X | X | X | X | X | X | | | | | | | | X | |
| Blood sampling ^f | | | | | | | | | See "Blood Samples Flow Chart and PK Blood Samples Flow Chart" (§2.3 § 2.4) | | | | | | | | |
| Cohort assignment | | | | X | | | | | | | | | | | | | |
| TLS Risk Assessment ^g | | | | X | | | | | | | | | | | | | |

| PROCEDURE | Pre-screening Period Day -112 to Day -28 | Screening Visit Day -27 to Day -1 | STUDY VISITS | | | | | | | |
|-------------------------------|---|--------------------------------------|----------------------|----------|-------------|---------|----------|-------------|----------|---------------------------------|
| | | | Cycle 1 | | | Cycle 2 | | | Cycle 3+ | End of Study Visit ^l |
| | | | Visit 1 ^k | | Visit 2 & 3 | Visit 1 | | Visit 2 & 3 | | |
| | | | Day 1 | Days 2-4 | Days 8 & 15 | Day 1 | Days 2-4 | Days 8 & 15 | | |
| TLS Prophylaxis ^b | | | X | | | X | | | | |
| Premedication ⁱ | | | X | | | X | | | | |
| Study drug administration | | | X | | | X | | | | |
| Adverse events | | X | X | X | X | X | X | X | | X |
| Concomitant medications | | | X | X | X | X | X | X | | X |
| Overall survival ^j | | | | | | | | | | X ^j |

a = Informed consent to undergo the study procedures, including the performance of the new biopsy, whenever possible.

b = Tumor/NHL assessment will be done, using RECIST v1.1 for Step 1 and Cheson Criteria (The Lugano Classification, 2014) for Step 2, based on CT/(PET)-CT scans or MRI not older than 2 weeks at Screening Visit, in the last 6 weeks (4+2 weeks) at Visit 1 (Day 1) prior to study drug administration and at the End of Study Visit. Images shall be repeated to allow tumor/NHL assessment every 2 cycles.

c = Ophthalmic or dermatologic visits to be performed and repeated bi-weekly in case of ocular or dermatological events higher than grade 1 during the study treatment period. The frequency of ocular or dermatological events can be increased upon Investigator's judgment.

d = Vital signs to be collected prior to study drug administration, every 15 minutes at Cycle 1 and every 30 minutes starting from Cycle 2 during the first hour of study drug administration and then at every hour until the end of infusion. In case of temporary infusion interruption, vital signs should be collected every 15 minutes until the first hour post-infusion re-start and then every hour until the end of infusion (or until 1-hour after the permanent infusion interruption).

e = 12-lead ECG record to be performed prior to study drug administration and 30 minutes after the end of the infusion; ECG will be also monitored during IV infusion up to 30 minutes after the end of infusion. If ECG monitoring equipment is not available, at Cycle 1 heart rate should be monitored

up to 30 minutes after the end of infusion and 12-lead ECG recorded at 30, 60 and 120 minutes during the IV infusion with final 12-lead ECG record at 30 minutes after the end of infusion; starting from Cycle 2, heart rate should be monitored up to 30 minutes after the end of infusion with final 12-lead ECG record at 30 minutes after the end of infusion.

f = See “Blood Samples Flow Chart and PK Blood Samples Flow Chart” (§ 2.3 and §2.4) that includes blood sampling for safety lab tests, β -HCG pregnancy test, Anti-HIV Antibodies, Anti-HBcAg antibodies, Anti-HBsAg antibodies, HBV-DNA, HCV-RNA tests, immunogenicity assessment, free CD205 assessment, flow Cytometry for CD205 expression and DNA sequence of CD205 assessment.

g = TLS Risk Assessment according to Investigator’s TLS manual, will be performed ONLY prior to study drug administration at Visit 1 (Day 1) of Cycle 1 (see Appendix II).

h = TLS prophylaxis should be given every cycle, if applicable (see Appendix II).

i = Mandatory premedication with an antihistaminic and an antipyretic (as per local practice), and dexamethasone 20 mg will be administered 30 to 60 minutes prior to study drug administration. Starting from Cycle 3, the dose of dexamethasone can be adjusted upon Investigator’s judgment.

j = After the End of Study Visit, all patients evaluable for efficacy will be followed for survival status according to local practice (a visit or a telephone call) every 12 weeks up to a period of 12 months after first treatment administration to the last patient.

k = At Visit 1 of Cycle 1, hospitalization is required until the completion of study procedures at 48 hours. Patient can remain hospitalized for the completion of the study procedures up to 72 hours. In addition starting from Cycle 2, hospitalization is not mandatory if the patient did not experience any infusion reactions or any adverse events during the administration at Cycle 1.

l = End of Study Visit planned within 6 weeks after the last administered dose or at the time of study withdrawal/treatment discontinuation of study drug.

